** Support T-cell based immune responses to newly exposed neoantigens.* Activity of checkpoint inhibitors is dependent on their being a pre-existing immune response to the cancer. Radiotherapy has the potential to engage immune responses to cancer by increasing the mutational load of tumors and in turn the expression of neoantigens needed to evoke the cytotoxic activity of T cells. Indeed there is strong evidence that neoantigens play a critical role in driving the strength of intratumoral T cell responses and may also influence tumor cell sensitivity to cancer immunotherapy (49). In this setting, anti-PD-1 has the

potential to regulate immunosuppression by augmenting the frequency and suppressive phenotype of myeloid cells within tumors post radiotherapy. It may also increase the function of newly activated tumor-reactive immune cells, by inhibiting PD-1 binding of its inhibitory ligand PD-L1; the expression of which can be induced within tumors by radiation therapy.

Whilst the overlapping toxicities of SABR and pembrolizumab are not yet fully understood, few are expected. Safety will be monitored carefully throughout the trial in all patients (n=16 per arm). We hypothesize that augmentation of immunity in this subgroup of patients may enhance long-term control of the disease. It is anticipated that the findings of this study will serve as the basis for larger randomised studies in the future.

4.14 Rationale for Dose Selection/Regimen/Modification

The choice of the 200 mg Q3W as an appropriate dose for the switch to fixed dosing is based on simulations performed using the population PK model of pembrolizumab showing that the fixed dose of 200 mg every 3 weeks will provide exposures that 1) are optimally consistent with those obtained with the 2 mg/kg dose every 3 weeks, 2) will maintain individual patient exposures in the exposure range established in melanoma as associated with maximal efficacy response and 3) will maintain individual patients exposure in the exposure range established in melanoma that are well tolerated and safe. On this basis the chosen dose of 200 mg q3 weekly represents an appropriate standard of care in the setting of previously treated NSCLC.

A fixed dose regimen will simplify the dosing regimen to be more convenient for physicians and to reduce potential for dosing errors. A fixed dosing scheme will also reduce complexity in the logistical chain at treatment facilities and reduce wastage. This dose is now the standard single-agent dose used in NSCLC and Head and Neck Cancer.

5. Trial Objectives

5.1 Hypothesis

This investigator driven Phase Ib study will examine the safety, efficacy and biological effects of two schedules of pembrolizumab, an antibody targeted against anti-programmed cell death 1 (PD-1), which will be given either before or after stereotactic ablative body radiotherapy (SABR) for metastatic NSCLC. We hypothesise that both arms i.e. 1) SABR followed by anti-PD-1 and; 2)anti-PD-1 with SABR after first cycle of pembrolizumab; will have clinically acceptable safety profiles with evidence of local and systemic efficacy; and that there will be differences in the immunological responses related to schedule of treatment.

5.2 Objectives

Primary objective:

To assess common toxicities associated with pembrolizumab in combination with SABR when SABR is given before or after first cycle of pembrolizumab in patients with metastatic NSCLC.

Secondary objectives:

Secondary objectives are to examine the clinical efficacy of the combination:

- To describe response rate in: a) lesions treated with SABR, b) non-irradiated lesions and c) overall response, and compare between treatment arms
- To describe overall survival (OS) and progression free survival (PFS) and compare between treatment arms
- To describe the event history (progression at an irradiated lesion, progression at a non-irradiated lesion, appearance of a new lesion, ceasing treatment and death) of NSCLC patients treated with SABR in combination with pembrolizumab

Exploratory Objectives

- Evaluate PD-L1 expression in baseline tissue using immunohistochemistry.
- Evaluate baseline and longitudinal cellular and molecular changes in archival tumour tissue, and/or fresh tumour biopsies. This will include tumour infiltrating lymphocytes (TILs), CD73 and other markers.
- Evaluate longitudinal changes in immunological cellular subsets and cytokines within peripheral blood.

5.3 Endpoints

Primary Endpoint

- Toxicities associated with SABR in combination to pembrolizumab are defined as adverse events (AE's) considered possibly, probably or definitely related to the treatment. Safety (acute and long term) will be assessed using CTCAE version 4.03.

Secondary Endpoints:

- Response will be assessed by 4 different methods (RECIST 1.1, irRECIST, Peter Mac Metabolic Response Criteria and PERCIST 1.0) and will be assessed a) only considering irradiated lesions; b) only considering non-irradiated lesions and; c) considering all lesions (overall response rate)
- Overall survival will be measured from the date of randomisation to the date of death from any cause.
- Progression free survival will be measured from the date of randomisation to the date of first progression at any site or date of death due to any cause.
- Event history is defined as the time from the date of randomisation to the date of each event of interest (progression at an irradiated lesion, progression at a non-irradiated lesion, appearance of a new lesion, ceasing treatment and death). Patients alive will be censored at the date of last follow-up.

Exploratory Endpoints

A number of translational endpoints will be evaluated including:

- PD-L1 expression in tumour tissue using immunohistochemistry with the 22C3 antibody using the DAKO Autolink 48 system.

- Tumour infiltrating lymphocytes (TILs).
- Changes in host anti-tumour immunity to look for evidence of immune activation and relief of immunosuppression in tumour tissue and peripheral blood from the patient over time and at time of progression (if this occurs).
 - Blood samples will be collected at multiple time points before, during and after trial related therapies. These will be analysed for biomarkers including, but not limited to, the following (this is a non-exhaustive list):
 - Absolute lymphocyte counts using a blood analyser.
 - The presence of CD8+ T cells by flow cytometric analysis.
 - Change in frequency of tumour reactive T cells. These may include markers for HLA-DR, CD4+, CD8+ T cells, PD-1, TIM-3 signifying antigen presentation and experience.
 - Immune cytokines

6. Trial Design

This is a prospective, open label, two arm randomised clinical trial with 1:1 allocation ratio evaluating the safety, efficacy and immunological effects of two different sequences of pembrolizumab in combination with SABR treatment in NSCLC – pembrolizumab given either before or after SABR.

Eligible patients will be randomised to either:

Arm 1: SABR followed by pembrolizumab; *or*

Arm 2: Pembrolizumab followed by SABR after cycle 1

Refer to Trial Schema

Pembrolizumab at a dose of 200 mg will be delivered every 3 weeks for a total duration of 102 weeks (34 cycles), commencing either 7 days (+/- 2 days) before the first dose of SABR or 7 days (+/-2 days) after the last dose of SABR.

Tumour response will be assessed according to RECIST 1.1, and irRECIST, Peter Mac Metabolic Response Criteria and PERCIST 1.0. Responses will be characterized in lesions treated with SABR and in un-irradiated lesions.

Peripheral blood samples and where possible, tumour tissue will be collected pre, during and post-treatment to assess baseline findings and longitudinal changes in immune subsets within tumour tissue and peripheral blood.

Evaluable patients are those that receive at least one dose of pembrolizumab and one dose of SABR. Non-evaluable patients will be replaced until the planned sample size has been reached.

7. Study Population

Patients with metastatic NSCLC who meet the inclusion/exclusion criteria described below will be eligible for participation in this study.

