Trial Phase:	Screening Phase	Treatment Phase			Follow-up Phase		Progression
Trial phase and windows	Screening -28 to -1	Day 1 Cycle 1 3 days \pm 2 days prior to the first dose of pembrolizumab	SABR 7 days \pm 2 days from cycle 1 day 1	Day 1 Cycle 2-34 3 days \pm 2 days prior to each dose of pembrolizumab	Safety Follow-up 30 days \pm 3 days from date of last dose of pembrolizumab	Follow-up 3 months \pm 7 days from the last cycle of pembrolizumab	Upon first progression ¹
Biochemistry ⁶	X	X		X		indicated	
Thyroid Function tests ⁷	X	X		X			
Coagulation profile ⁸	X	X		X			
Virology ⁹	X						
Tumour Evaluation							
CT scan (Brain, Chest, Abdo, Pelvis) reported with RECIST 1.1 or MRI ¹⁰	X			X		X	
Whole body bone scan ¹⁰ (if clinically indicated)	X			X		X	
Response assessment ¹⁰				X		X	
FDG-PET ¹⁰	X			X ¹¹			
Translational studies							
Fresh tumour biopsy sample ¹²	X					X	X
Archival tumour biopsy sample ¹³	X						
Blood Collection ¹⁴ (serum and ctDNA)		X	X	X		X	X

Table 1 and 2 Footnotes

1. Beyond first progression, every effort should be made to record results of subsequent tumour assessments. In addition, details of any new anti-cancer treatment commenced is to be collected.
2. Vital signs include blood pressure, heart rate, respiratory rate and temperature. Body measurements including height and weight (height only required at screening).
3. Urine or serum pregnancy test for patient of childbearing potential should be performed within 7 days randomisation and also 72 hours before first dose of pembrolizumab. If the urine test is positive or cannot be confirmed as negative, a serum pregnancy test will be required.
4. Baseline abnormalities must be recorded from signature of informed consent to prior to start of treatment. Adverse events (using CTCAE v4.03) are then required to be reported on completion of SABR, day 1 of every pembrolizumab cycle and at every follow-up visit. If at any time, a patient commences a new anti-cancer therapy, recording of adverse events is no longer required.

Laboratory Procedures/Assessments – All diagnostic laboratory tests should be performed within 10 days of randomisation (to determine eligibility), and also on day 1 ± 3 days of every cycle of pembrolizumab (unless otherwise specified)

5. Haematology: Haematocrit, haemoglobin, platelet count, white blood cell count (total and differential), red blood cell count, absolute neutrophil count and absolute lymphocyte count.

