6. Biochemistry: calcium chloride, glucose, phosphorus, potassium, sodium, magnesium, total protein, Liver Function Tests: Albumin, Alkaline Phosphatase (ALP), Alanine Aminotransferase (ALT), Aspartate Aminotransferase (AST), Lactate Dehydrogenase (LDH), Gamma-Glutamyl Transferase (GGT), total bilirubin (+direct bilirubin if total bilirubin is elevated above the ULN), Kidney Function Tests: Urea, creatinine.
7. Thyroid Function tests: T3, T4 and TSH. To be performed at during screening, day 1 cycle and every 6 weeks thereafter.
8. Coagulation Profile: PT (INR), aPTT.
9. Virology: HIV, Hepatitis B and C tests only required for those patients at risk of prior or current active infection as determined by the investigator. To be performed within 21 days of randomisation.

Tumour evaluation

10. Radiological tumour assessments will be performed by CT scan (or MRI as required if tumour is in extremity) at screening (within 6 weeks of randomisation), prior to cycle 3, 5, 7 and every 3 cycles thereafter in the treatment phase. Then 3 monthly in the follow-up phase until the last patient recruited completes 24 months of follow-up, unless evidence of progression earlier. Whole body bone scan (WBBS) will be performed if clinically indicated at the same time points. Formal response assessment (using RECIST 1.1, irRECIST, Peter Mac Metabolic Response Criteria and PERCIST 1.0.) at each scheduled scan time point. Response should be confirmed with repeat imaging 4 to 8 weeks later by the same imaging modality. CT of brain only required at screening.
11. FDG PET at baseline and prior to cycle 5 of pembrolizumab. (note: a contemporaneous CT brain/chest/abdo pelvis performed at the same time will fulfill the CT requirement 3 month follow-up)

Biological Evaluations

12. A fresh biopsy of the primary or metastatic lesion will be performed at screening (within 12 weeks of randomisation). and 3 months post completion of SABR. This will ideally be the same site as biopsied before at screening. In event of disease progression, a sample from progressing metastatic site(s), if feasible, is requested. Refer to the SABRseq laboratory manual for further details on handling and shipping of tumour samples.

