8.6 Survival Follow-up

Patients who discontinue trial treatment due to progression, progress during follow-up or commence a new systemic treatment will be followed for survival only. Survival status will be assessed every 3 months until death, withdrawal of consent, or the end of the study, whichever occurs first. Where possible, every effort should be made to record results of subsequent tumour assessments and any new anti-cancer therapies.

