14.6 Time-to-Event Endpoint Analysis

A cut-off date for follow-up will be determined at the time of analysis. The cut-off date will be chosen to enable data on follow-up to that date to be collected, where possible, on all living patients. All events occurring after this date will be ignored in the analysis in order to minimise reporting bias. Progression free survival and overall survival will be described for each arm using Kaplan-Meier methods. Estimates at key time points will be provided with 95% confidence interval. Stratified log-rank test will be used to compare the curves between arms.

An event history chart will be used to describe the individual patient's events of interest. Each patient in each arm will be represented as a line with different symbols identifying when the patient had a progression on irradiated lesions, progression on a non-irradiated lesions, appearance of new lesions, when treatment ceased, when they died and when censoring occurred.

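### Living patients are censored at last follow-up for imaging-detected progression, and PFS has no other censoring date, so time without scans can appear progression-free

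*Combined protocol and SAP*

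**What the plan says.** Event history is a secondary endpoint. Section 5.3 states: "Event history is defined as the time from the date of randomisation to the date of each event of interest". The events listed are progression in irradiated lesions, progression in non-irradiated lesions, new lesions, stopping treatment, and death. The next sentence is "Patients alive will be censored at the date of last follow-up". It is the only censoring rule in 5.3 and it does not mention a tumour assessment. PFS is defined in the same section, from randomisation to first progression anywhere or death, without a censoring date. Section 14.6 adds only a common cut-off, chosen so that follow-up to that date can be collected, where possible, on everyone still alive.

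On imaging, footnote 10 to the Schedule of Events reads: "Then 3 monthly in the follow-up phase until the last patient recruited completes 24 months of follow-up, unless evidence of progression earlier". Section 8.5 ends the follow-up phase at progression or new anti-neoplastic therapy. Section 8.6 then states: "Patients who discontinue trial treatment due to progression, progress during follow-up or commence a new systemic treatment will be followed for survival only". It adds: "Where possible, every effort should be made to record results of subsequent tumour assessments and any new anti-cancer therapies". Footnote 1 to the schedule makes a similar request: "Beyond first progression, every effort should be made to record results of subsequent tumour assessments". Section 10.2 lets pembrolizumab continue after radiological progression in selected patients.

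On analysis, 14.6 applies Kaplan-Meier estimates with confidence intervals and a stratified log-rank test to PFS and OS only. Event history is shown as one line per patient, with symbols for each type of progression, the end of treatment, "when they died and when censoring occurred". There is no symbol for the last scan.

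**The concern.** Last follow-up is the right censoring date for death, because a survival contact tells us whether the patient is alive. It is the wrong date for an event that can be seen only on a scan. Once scheduled imaging has ended, each later survival contact moves the censoring date forward and adds no information about the lesions.

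Two things are at stake. On the event history chart, a line without a local-progression symbol up to its censoring mark may be scanned throughout or may include many months without a scan, and the reader cannot tell which. Long-term local and distant control is the stated treatment aim (9.2), so readers will look for it there. For PFS the issue reaches a planned estimate and a planned test between arms of 16 patients.

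**Working it through.** **1. The plan's own figures.** The plan states no figure for event history or local control. Its sample size rests on Table 9, which reproduces: at a true rate of 10%, 1 − 0.90^16 = 0.815 per arm and 1 − 0.90^32 = 0.966 overall. No censoring date enters that calculation.

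**2. Who can be censored later than the last scan.**

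| Patient | Scheduled scans | Can last follow-up run past the last scan? |
|---|---|---|
| Stops treatment without progression or new therapy | 3-monthly (8.5, footnote 10) | Only by missed scans |
| Continues pembrolizumab after radiological progression (10.2) | Treatment-phase scans | Only by missed scans |
| Stops treatment for progression, or progresses in follow-up | End (8.5, 8.6, footnote 10) | Yes, for the lesion events not yet seen; the PFS event has occurred |
| Starts new systemic therapy before progression | End (8.5, 8.6) | Yes, for lesion events and for PFS |

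**3. PFS: what one patient in the last row can do.** Take a hypothetical patient whose last scan is at month 4, who then starts new therapy and is alive at month 26. Last-follow-up censoring shows 26 progression-free months and last-scan censoring shows 4, a difference of 22. Assume 16 patients in the arm, the other 15 fully followed, no event before month 4, and k events among those 15 by some later time before month 26.

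- Kept at risk: S = (16 − k)/16
- Censored at the last scan: S = (15 − k)/15
- Difference: k/15 − k/16 = k/240

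For k = 8 this is 50.0% against 46.7% (3.3 points). For k = 12 it is 25.0% against 20.0% (5.0 points). The most it can be is k = 15, giving 15/240 = 6.25 points. Events before month 4 make it smaller. Two such patients give k/14 − k/16 = k/112, or 7.1 points at k = 8. The documents give no basis for the expected number.

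**4. Lesion-specific events: illustration only, since no such estimate is planned.** A simulation of 400,000 patients per scenario compared 24-month Kaplan-Meier local control under the two rules. Inputs from the documents:

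- Local control of 71% (the low end for liver metastases in 4.2, taken as a 24-month rate by assumption) or 91% (2-year figure for primary lung cancer in 4.3). The monthly hazard is −ln(control)/24, which is 0.0143 or 0.0039.
- Median time to progression elsewhere of 3.0, 6.0 or 10.3 months (median PFS figures in 4.12, used as stand-ins).

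Assumptions not in the documents: exponential and independent times; a median of 10 months from progression elsewhere to death; cut-off uniform between 24 and 48 months; continuous scanning until it stops; deaths censored at the date of death. The last assumption also counts unscanned time before death, which goes further than the sentence in 5.3 on living patients.

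| True control | Median (months) | Unscanned share of first 24 months* | Last follow-up, no later scans | Last follow-up, half still scanned | Last scan* |
|---|---|---|---|---|---|
| 71% | 3.0 | 71% | 93.2% | 82.2% | 70.9% |
| 71% | 6.0 | 52% | 87.2% | 78.9% | 71.2% |
| 71% | 10.3 | 37% | 82.0% | 76.6% | 71.0% |
| 91% | 3.0 | 71% | 98.1% | 94.5% | 90.9% |
| 91% | 6.0 | 52% | 96.2% | 93.6% | 91.0% |
| 91% | 10.3 | 37% | 94.5% | 92.8% | 90.9% |

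*With no later scans.

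The excess is 3.5 to 22.2 points with no later scans (94.5 − 91 to 93.2 − 71) and 1.8 to 11.2 points if half are still scanned (92.8 − 91 to 82.2 − 71). It is zero if everyone is still scanned.

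**The case against.** The strongest reply is that nothing planned depends on lesion-specific censoring. Section 14.6 only charts event history, and no local-control rate, cumulative incidence or test is specified. That stands. A reader might infer that the trial's local-control result will be overstated, but the documents contain no such result.

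Second, survival-only contact does not follow every first progression. Patients treated beyond progression under 10.2 stay on the treatment-phase schedule, although 8.3.3 qualifies Arm 2 scans by clinical indication. Sections 8.6 and footnote 1 also ask that later assessments be recorded. That stands as a limit on the size. It does not remove the problem, because recording what happens to be done is not a scan schedule.

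Third, last follow-up might mean the last visit of the 8.5 follow-up phase, which includes imaging. That reading fails because the same sentence also has to serve for death, where 8.6 contacts must count.

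Fourth, the censoring sentence belongs to the event-history endpoint, and for PFS most patients moved to survival-only contact have already had the event. This is largely right. The exposure is mainly patients who start new therapy before progression. With no other rule stated, last follow-up is the date an analyst would take for them.

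A reader might also subtract median PFS from median OS in 4.12 and conclude that each patient contributes 16.2 − 6.0 = 10.2 unscanned months (9.3 − 3.0 = 6.3 if previously treated). The documents do not support this. A difference of medians is not a per-patient duration, much of that time is lived by patients who die and so are not censored under this rule, and it assumes that nobody is scanned after progression. Nor do the documents give figures showing that most first failures will lie outside the SABR field.

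**Conclusion.** The point holds in a limited form. The plan states a censoring rule that suits death and applies it to events detected by imaging, while scheduled imaging ends for a defined group of patients. For that group the chart can show unscanned time as freedom from lesion progression. PFS can be lengthened in the same way, mainly in patients who start new therapy before progression.

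The number of PFS cases cannot be derived from the documents. One case moves an arm's curve by at most 6.25 points under the assumptions in step 3 of the working, and the shift goes to whichever arm the patient is in. The 3.5 to 22.2 points for local control would apply only to an estimate that someone adds later, and only under the simulation's assumptions. The primary safety endpoint, the sample size and OS are not affected.

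**What to change.** In 5.3 and 14.6, state that PFS and each lesion-specific progression time are censored at the last adequate tumour assessment, and that the date of last contact is used for death only. Say in the same place how a death after scanning has stopped counts towards PFS. On the event history chart, mark the last scan on each line separately from the last survival contact. If a lesion-specific rate is estimated later, treat death as a competing event.

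The cost is a few sentences and one extra chart symbol. Scan dates come from assessments already scheduled, and no visit is added. The downside is slightly shorter follow-up for progression. Last-scan censoring can also be informative if stopping scans is related to failure. The close agreement of the last-scan rule with the truth in the illustration depends on assumed independence, so showing PFS under both dates as a sensitivity analysis would be a sensible addition.
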